4.4 Early Withdrawal of Subjects

4.4.1 When and How to Withdraw Subjects

Subject may be withdrawn from the study prior to the expected completion of the protocol if the subject fails to adhere to protocol requirements, subject withdraws consent, or symptoms of acute rhinosinusitis exacerbation persist. Subjects will return to routine clinical care at that point.

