4.4.2 Data Collection and Follow-up for Withdrawn Subjects

Even though subjects may be prematurely withdrawn from the study, it is imperative to collect infection data (microbiology swabs) or symptomatic data. Such data is important to the integrity of the final study analysis since early withdrawal could be related to the tolerability profile or the ineffectiveness of the therapy. If a subject withdraws consent to participate in the study, attempts should be made to obtain permission to follow up with the subject's CRS for the duration of the 12-week follow-up period. Subjects with incomplete/missing data will not be included in the analysis.

5 Study Drug

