6.5 Statistical Methods

Data will be analyzed after 100 subjects have completed the study. Descriptive demographic data will be compiled including mean and median age, adjuvant therapy use, use of oral antibiotics, and microbiome profile. Longitudinal linear mixed effects modeling will be used to examine the relationship between all outcome measures and treatment assignment, assuming that the distribution of the outcome measures follow a unimodal symmetric distribution and satisfies the assumptions for mixed effects modeling. Mixed effects modeling takes advantage of all available data (up to the point of loss to follow-up or withdrawal) and also can address missing data. As long as the level of missingness is not excessive and patterns of missingness are not detected, mixed effects modeling can use all available data.²¹⁻²⁴ For all analyses, alpha will be set to 0.05 (two-sided).

The Epidemiology Department may be consulted at the completion of the study to assist with data analysis. Only de-identified data will be provided. No PHI will be shared.

CONFIDENTIAL

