6.6 Subject Population(s) for Analysis

All-randomized population: Any subject randomized into the study, regardless of whether they received study drug, will be analyzed.

7 Safety and Adverse Events

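### Data sought after early withdrawal have no stated place in the analysis: 6.5 describes model data only up to withdrawal, and 4.4.2 excludes incomplete subjects, against 4.4.2's own purpose and the all-randomized population in 6.6

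*Combined protocol and SAP*

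**What the plan says.** Four statements bear on a subject who stops early.

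- **Reasons for withdrawal (4.4.1).** These are non-adherence, withdrawal of consent, or that "symptoms of acute rhinosinusitis exacerbation persist". The last is close to the outcome itself.
- **Collection after withdrawal (4.4.2).** For subjects withdrawn early, "it is imperative to collect infection data (microbiology swabs) or symptomatic data". The reason given is: "Such data is important to the integrity of the final study analysis since early withdrawal could be related to the tolerability profile or the ineffectiveness". Where consent is withdrawn, "attempts should be made to obtain permission to follow up with the subject's CRS for the duration of the 12-week follow-up period".
- **Exclusion (4.4.2, last sentence).** "Subjects with incomplete/missing data will not be included in the analysis".
- **Data in the model (6.5) and population (6.6).** Section 6.5 says: "Mixed effects modeling takes advantage of all available data (up to the point of loss to follow-up or withdrawal". It adds that the model can use all available data if missingness is not excessive and shows no pattern. Section 6.6 says: "Any subject randomized into the study, regardless of whether they received study drug, will be analyzed".

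No section says how a value obtained after withdrawal enters any analysis.

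**The concern.** The plan holds three rules that cannot all apply: complete subjects only (end of 4.4.2), data up to withdrawal (6.5), and everyone randomized (6.6). Under either of the first two, the values that 4.4.2 considers important for the final analysis would not reach it.

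The cut-off is not neutral. Persistent symptoms are a ground for withdrawal, and 4.4.2 itself expects withdrawal to follow tolerability or lack of effect. Setting aside values that were observed replaces them with an assumption that withdrawn subjects would have fared like similar subjects who stayed. That assumption cannot be tested from the data kept, and the plan gives a reason to doubt it. At stake is whether the between-arm estimate describes all randomized subjects or mainly those who remained.

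**Working it through.** **1. The plan's own figure.** Section 6.4 gives SD 20, a 95% CI half-width of 10, and 32 per group. The half-width for a difference of two means is t(0.975, 2n−2) × SD × √(2/n). At n = 31 it is 10.16; at n = 32 it is 9.99. The 32 per group reproduces.

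**2. The margin.** Two groups of 32 make 64. Against 100 recruited, the margin is 36/100 = 36%. Section 4.3 assigns the first 10 subjects to treatment without randomization; if only 90 are randomized, it is 26/90 = 28.9%. Section 6.4 meant this to cover error, early withdrawal and non-compliance together.

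**3. What each rule keeps for a subject who withdraws but still gives later values.**

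| Time of withdrawal | 6.5 as written | End of 4.4.2 | Purpose of 4.4.2, with 6.6 |
|---|---|---|---|
| Before week 4 | Baseline only | Excluded if any item is missing | Baseline plus later values |
| Between weeks 4 and 12 | Baseline and week 4 | Excluded if any item is missing | Baseline, week 4 and later values |

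A subject with only a baseline value adds almost nothing to the treatment contrast.

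**4. Illustrative size.** From 6.4: SD 20. Assumed, because the documents do not give them: baseline correlation 0.5, a 10-point SNOT-22 effect on quinine, 50 per arm, all withdrawals before week 4, and a baseline-adjusted comparison at one time point. The residual SD is 20 × √(1 − 0.5²) = 17.3. With all values kept, the SE is 17.3 × √(2/50) = 3.5.

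*Random withdrawal, drug effect lost.* The all-randomized effect is 10 × (1 − w), where w is the proportion withdrawn. The cut-off analysis estimates 10.

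| w | All-randomized | Cut-off | Gap | Gap / 3.5 |
|---|---|---|---|---|
| 10% | 9.0 | 10 | 1.0 | 0.3 |
| 18% | 8.2 | 10 | 1.8 | 0.5 |
| 36% | 6.4 | 10 | 3.6 | 1.0 |

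Simulation agrees within about 0.2 points.

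*Poor responders withdraw at one threshold common to both arms, effect kept.* More placebo than quinine subjects cross the threshold, so the retained placebo mean improves more and the contrast shrinks. For a sharp threshold on the baseline-adjusted score:
- With 18% of placebo withdrawn, the cut is 0.915 residual SDs above the placebo mean.
- For quinine the cut is 0.915 + 10/17.3 = 1.493, so 6.8% withdraw.
- The retained means improve by 0.320 and 0.140 SDs, from φ(c)/Φ(c) at each cut c.
- The contrast is 10 − 17.3 × (0.320 − 0.140) = 6.9, against 10 in all randomized subjects.

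Other threshold settings give other sizes: one run with 18% of placebo and 9% of quinine subjects withdrawn gave 7.9. Only the direction is robust.

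*Poor responders withdraw in equal proportions by arm.* Both retained means improve equally. If the effect is kept there is no bias: 10 against 10. If the effect is lost, the result matches the random case.

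**The case against.** The strongest reply is that 6.5 contains no discard rule. Its parenthesis describes a property of mixed models, pairs withdrawal with loss to follow-up, and may simply mean the point where observation ends. On that reading, data collected under 4.4.2 are available data and the two sections agree. A reader might infer that the plan collects these outcomes and then orders them dropped. The documents do not say that. What stands is that this is the only statement of which records enter the model, it ends at withdrawal, and nothing else brings later values in.

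Several limits on the point are also right:

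- **What is collected.** Section 4.4.2 names swabs or symptom data. It does not promise a SNOT-22 at weeks 4 and 12 for withdrawn subjects, who return to routine care, and follow-up after withdrawal of consent needs permission. Some values will be truly missing whatever 6.5 says.
- **Who is affected.** It would go too far to say that only subjects who stayed are compared. Anyone withdrawing after week 4 keeps the week 4 value.
- **The explicit exclusion is in 4.4.2.** Editing 6.5 alone would leave it in force, and many withdrawn subjects would still be removed. The two must be fixed together.
- **The arithmetic.** It uses one time point, not the planned longitudinal model. The 10-point effect is assumed; 6.4 uses 10 only as a half-width. In the random case the gap is a difference between two target effects. It is an overstatement only if the target is the effect in everyone as randomized, which 6.6 suggests but does not define.
- **Rescue.** Some later values may follow antibiotics started under 5.6, and need for antibiotics is itself a primary outcome, so part of this failure is captured there.

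**Conclusion.** The point holds as a conflict between sections that should be resolved before analysis. Read as written, the 6.5 description and the last sentence of 4.4.2 both run against the reason 4.4.2 gives for following withdrawn subjects and against 6.6.

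The consequence is modest at low withdrawal in the random case (about 0.3 SE at 10%), where it grows to about 1 SE at 36%. Those figures rest on the stated assumptions and on every withdrawal falling before week 4. The 36% is the combined margin in 6.4, not an expected withdrawal rate, and exceeds the 28.9% available if 90 are randomized.

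A reader might also infer that the cut-off favours quinine. The documents do not support a direction: the bias can overstate the effect, understate it or vanish, depending on who withdraws and whether the effect persists.

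**What to change.** 1. In 6.5, remove the reference to withdrawal from the parenthesis. State that all SNOT-22 and culture results actually obtained through week 12, including those collected after early withdrawal with the subject's permission, enter the all-randomized analysis under the assigned arm.
2. In 4.4.2, delete the final sentence excluding subjects with incomplete or missing data, or reconcile it with 6.5 and 6.6.
3. Keep the analysis cut at withdrawal as a sensitivity analysis.
4. Say in 6.5 that values after rescue antibiotics follow whatever analysis rule the trial sets for rescue, so that the new sentence does not settle that question by default.

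The cost is a few sentences and one added analysis. No new procedures are needed, because the change covers only results actually obtained. The downside is that the all-randomized estimate may be smaller than the estimate in subjects who stayed on treatment; the sensitivity analysis shows by how much.

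### Section 6.5 attaches to the mixed model a missing-data condition that is undefined and stricter than the model needs, and section 4.4.2 separately excludes subjects with incomplete data, contradicting 6.5 and 6.6

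*Combined protocol and SAP*

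**What the plan says.** Section 6.5 (Statistical Methods) names longitudinal linear mixed-effects modelling for all outcome measures. It describes the method's use of data thus: "Mixed effects modeling takes advantage of all available data (up to the point of loss to follow-up or withdrawal) and also can address missing data". It then adds a proviso, that the model can use all available data "As long as the level of missingness is not excessive and patterns of missingness are not detected". No threshold defines excessive, no test defines a pattern, and no action follows if either is found.

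Section 4.4.1 begins "Subject may be withdrawn from the study prior to the expected completion of the protocol" and lists among the grounds that "symptoms of acute rhinosinusitis exacerbation persist". Section 4.4.2 recognises that "early withdrawal could be related to the tolerability profile or the ineffectiveness of the therapy" and calls for infection or symptom data on withdrawn subjects. Where consent is withdrawn, it adds that "attempts should be made to obtain permission to follow up with the subject's CRS for the duration of the 12-week follow-up period". The same section ends: "Subjects with incomplete/missing data will not be included in the analysis".

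Section 6.6 defines an all-randomized population in which every randomized subject is analyzed, whether or not study drug was received.

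**The concern.** The proviso in 6.5 is wrong in two directions. First, it comes close to requiring data missing completely at random. A likelihood-based mixed model is valid under the weaker MAR condition, in which missingness may depend on scores that were observed and are in the model. A detected pattern of that kind is what the method handles. Second, detecting no pattern is no reassurance about missingness that depends on values nobody recorded, and the plan has no sensitivity analysis for that case.

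This matters here because a listed ground for withdrawal is close to what SNOT-22 and endoscopy measure. A pattern is therefore foreseeable, and an analyst who finds one has no instruction. The only other missing-data rule on paper is the exclusion in 4.4.2, which cannot be followed together with 6.5 and 6.6. If it were followed, subjects doing badly would drop out of the comparison, and the estimated effect on a primary outcome could be distorted.

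**Working it through.** **Inputs from the documents.** SNOT-22 SD of about 20, half-width 10 for the 95% CI, 32 per group, 100 in total (section 6.4); ten non-randomized lead-in subjects (section 4.3); visits at weeks 0, 4 and 12 (section 3.1); two-sided alpha 0.05 (section 6.5).

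**The plan's own figure.** Half-width = t(0.975, 2n-2) × SD × √(2/n). With n = 32: 1.999 × 20 × √(2/32) = 9.995. With n = 31 it is 10.16. The stated 32 reproduces, and nothing below changes it.

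**Assumed, not in the documents.** True difference (quinine minus placebo) of -10 at weeks 4 and 12; correlation ρ between visits of 0.5 or 0.7; the withdrawal mechanisms below; no scores after withdrawal.

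**Scenario A: sharp cut-off.** Means at weeks 4 and 12 are 40 on placebo and 30 on quinine. Everyone whose week-4 score is at or above c withdraws. For those who stay, with a = (c - week-4 mean)/20 and λ = φ(a)/Φ(a), the expected week-12 score is the arm mean minus ρ × 20 × λ. The completers-only difference is therefore -10 + 20ρ(λ placebo - λ quinine).

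| c | Withdrawn, placebo / quinine | λ placebo | λ quinine | ρ = 0.5 | ρ = 0.7 |
|---|---|---|---|---|---|
| 50 | 31% / 16% | 0.509 | 0.288 | -7.8 | -6.9 |
| 55 | 23% / 11% | 0.389 | 0.204 | -8.1 | -7.4 |
| 60 | 16% / 7% | 0.288 | 0.139 | -8.5 | -7.9 |

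For example, with c = 50 and ρ = 0.7: -10 + 20 × 0.7 × (0.509 - 0.288) = -6.9. The loss runs from (10 - 8.5)/10 = 15% to (10 - 6.9)/10 = 31%. A simulation of the same set-up with 400,000 per arm agrees to within about 0.1, and its MAR regression estimate, which uses all observed scores, is -9.96 to -10.10.

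**Scenario B: graded withdrawal.** This simulates 45 per arm (90 randomized, if the ten lead-in subjects count toward the 100) with 4,000 replicates. Placebo means are 50, 45 and 40; quinine means are 50, 35 and 30. The chance of withdrawing after week 4 rises with the score on a logistic scale (0.08 per point), set to 10, 20 or 30% overall. Maximum likelihood (ML) regresses week 12 on arm, baseline and week 4 among those observed, then averages over everyone. The pattern check is a t-test at 0.05 of week-4 scores, leavers against stayers.

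| Withdrawal driven by | ρ | Rate | Completers only | ML | Pattern flagged |
|---|---|---|---|---|---|
| Observed week-4 score | 0.5 | 10 / 20 / 30% | -9.5 / -9.1 / -8.7 | -10.1 / -10.0 / -9.9 | 96 / 100 / 100% |
| Observed week-4 score | 0.7 | 10 / 20 / 30% | -9.1 / -8.6 / -8.2 | -10.0 / -10.0 / -9.9 | 96 / 100 / 100% |
| Unseen week-12 score | 0.5 | 10 / 20 / 30% | -8.6 / -8.2 / -7.6 | -9.0 / -8.7 / -8.2 | 49 / 68 / 75% |
| Unseen week-12 score | 0.7 | 10 / 20 / 30% | -8.7 / -8.0 / -7.4 | -9.4 / -9.0 / -8.7 | 76 / 92 / 96% |

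When withdrawal follows the observed score, completers-only analysis loses 5% (-9.47) to 18% (-8.24), and ML is unbiased within simulation error. A pattern is nonetheless flagged in nearly every trial. When withdrawal follows the unseen score, ML itself loses 6% (-9.43) to 18% (-8.22), and the check misses the pattern in up to 51% of trials. The condition in 6.5 therefore tends to fail where the model works, and it can pass where the model does not.

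**The case against.** The strongest reply is that 6.5 commits to the mixed model and that the proviso only describes, with references, what the method can do. That is right about the text. A reader might infer that the plan would set the model aside once a pattern appeared and fall back on completers. The documents do not say so: no switch is written, and the exclusion in 4.4.2 is unconditional and not linked to the proviso. It follows that deleting the proviso alone would leave the exclusion in force, and that the sizes calculated above belong to the exclusion, not to the proviso.

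A reader might also infer that the condition must fail by design. Withdrawal is discretionary under 4.4.1 and further data are sought under 4.4.2, so failure is foreseeable but not certain. Nor is it established that exclusions would fall mainly on the worse arm. Section 4.4.2 names tolerability beside ineffectiveness, and tolerability withdrawals could be heavier on either side.

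Caution about missingness is not misplaced in itself. Section 5.6 has patients who feel worse return for evaluation, and no study score is scheduled for such a visit. If that visit prompts withdrawal, MAR may not hold, and the mixed model is biased as in the lower half of the second table. This stands, and it is the reason for a sensitivity analysis. It does not rescue the proviso, which cannot detect the problem reliably.

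**Conclusion.** The point holds in this form. Section 6.5 contains an undefined condition, stricter than MAR, with no stated consequence and no check on missingness that depends on unobserved values. The exclusion in 4.4.2 contradicts the use of all available data in 6.5 and the all-randomized population in 6.6. If the exclusion were applied and withdrawal followed the week-4 score, the SNOT-22 effect would shrink by roughly 5 to 31% of an assumed 10 points, while a MAR likelihood analysis would stay near -10. The range reflects the withdrawal mechanism and rate. Only the SD of 20 comes from the protocol; the effect, correlation, mechanism and rate are assumptions. The 31% end requires everyone above a cut-off to leave with no later data, which is more severe than the discretionary wording of 4.4.1. The plan should be amended, but neither the sample size nor alpha is affected.

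**What to change.** 1. In 6.5, delete the proviso about excessive missingness and detected patterns. State that the mixed model for the continuous outcomes is fitted to all observed data from all randomized subjects under MAR, whatever pattern is seen.
2. In 4.4.2, delete the closing sentence that excludes subjects with incomplete or missing data, so that it agrees with 6.5 and 6.6.
3. Say whether scores collected after withdrawal enter the model. Section 6.5 describes data only up to loss to follow-up or withdrawal. Including later scores, some possibly after rescue antibiotics, changes what is estimated.
4. Add one missing-not-at-random sensitivity analysis for SNOT-22: multiple imputation of missing post-withdrawal scores with a pre-specified range of delta shifts.

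The cost is revised wording and one extra analysis. The main result will rest on MAR, which is credible only so far as the scores that prompt withdrawal are recorded and modelled. It should not be assumed that post-withdrawal SNOT-22 scores will exist: 4.4.2 asks for swabs or symptom data without naming that questionnaire, and its follow-up to week 12 after consent is withdrawn depends on permission.

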8.1	CONFIDENTIALITY.....	12
8.2	SOURCE DOCUMENTS	12
8.3	CASE REPORT FORMS.....	12
8.4	RECORDS RETENTION	12
9	STUDY MONITORING, AUDITING, AND INSPECTING	12
9.1	STUDY MONITORING PLAN.....	12
9.2	AUDITING AND INSPECTING	13
10	ETHICAL CONSIDERATIONS	13
11	STUDY FINANCES	13
11.1	FUNDING SOURCE.....	13
11.2	CONFLICT OF INTEREST	13
11.3	SUBJECT STIPENDS OR PAYMENTS	13
12	PUBLICATION PLAN	13
13	REFERENCES	14

CONFIDENTIAL

List of Abbreviations

CRS	Chronic Rhinosinusitis
NO	Nitric Oxide
FESS	Functional Endoscopic Sinus Surgery
HUP	Hospital of the University of Pennsylvania
CRF	Case Report Form
AE	Adverse Event
SAE	Serious Adverse Event
IDS	Investigational Drug Service

CONFIDENTIAL

Study Summary

Title	Efficacy and Safety of Adjuvant Topical Irrigation in the Treatment of Acute Exacerbation of Chronic Rhinosinusitis Following Functional Endoscopic Sinus Surgery (FESS)
Short Title	Topical Irrigation Therapy for CRS
Protocol Number	821731
Phase	II
Methodology	Randomized, double-blinded, placebo-controlled clinical trial.
Study Duration	3 years for accrual and follow up (+1 year for data analysis)
Study Center(s)	Single-center: Dept. of Otorhinolaryngology at HUP
Objectives	To evaluate the physiological differences between quinine-saline vs sucrose octaacetate-placebo nasal irrigations in subjects with CRS (both with and without polyps) as well as allergic fungal sinusitis.
Number of Subjects	Number of subjects projected for the entire study: 100
Diagnosis and Main Inclusion Criteria	Chronic Rhinosinusitis post FESS
Study Product, Dose, Route, Regimen	Nasal instillation of quinine sulfate and saline solution using a 3cc syringe adopted with an atomizer.
Duration of administration	Total duration of drug product administration (including any open-label lead-in, if applicable) is twice/day for 28 days.
Reference therapy	Desroisiers et al. (2001) findings showed that topical quinine in saline nasal solution was comparable, if not better to topical tobramycin (a commonly used antibiotic) for treatment of bacterial sinusitis.
Statistical Methodology	Longitudinal linear mixed-effects models to evaluate pre- and post-treatment continuous outcome scores.

CONFIDENTIAL

1 Introduction

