2.1 Primary Outcome Variable(s)

CONFIDENTIAL

The primary outcomes variables are:

- Pre- and post-treatment endoscopically guided sinonasal microbiologic cultures
- Pre- and post-treatment nasal endoscopy scored with the Lund-Kennedy scoring system by a blinded investigator¹⁸.
- Pre- and post-treatment quality of life questionnaires (22-item Sinonasal Outcomes Test [SNOT-22]).
- The necessity for rescue oral antibiotics for persistent infection.

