3.2 Primary Study Endpoints

- Efficacy of quinine and saline irrigations compared to saline irrigations alone.
- Changes in quality of life (SNOT-22 questionnaire) (both composite and subscale scores)
- Nasal endoscopy (Lund-Kennedy Score)
- Alterations in microbiology recovered (as determined by sinus microbiology culture)
- Whether or not conventional antibiotics were needed to treat the infection during or following the irrigation trial (as prescribed as part of routine care)

CONFIDENTIAL

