6.4 Sample Size Determination

There is no prior data to base a power calculation on. This trial will utilize a total of 100 patients to help guide future studies with appropriate power. In order to determine this sample size, we utilized a calculation that would ensure us that our confidence interval has a specified width. A previous study sampled over 300 CRS patients and found pre- and post-surgical SNOT-22 scores to have a standard deviation of about 20²¹. Based on this prior work, we estimate the required sample size to detect an effect with a precision of 10 (half the width of the desired 95% CI) to be 32 patients in each group. We will therefore recruit a total of n=100 patients in order to provide a margin for error, early withdrawal, or non-compliance.

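### Four unranked primary outcomes at two-sided 0.05, with no lead outcome, primary visit, success rule or adjustment, so nothing in the documents fixes before unblinding what a positive efficacy result is

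*Combined protocol and SAP*

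**What the plan says.** Section 2.1 opens its list with "The primary outcomes variables are" and gives four items: endoscopically guided cultures, the Lund-Kennedy score, SNOT-22 and the need for rescue oral antibiotics. None is marked as leading.

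Section 3.2 repeats the four as primary endpoints and widens one of them: "Changes in quality of life (SNOT-22 questionnaire) (both composite and subscale scores". The antibiotic item there reads "Whether or not conventional antibiotics were needed to treat the infection during or following the irrigation trial". Section 3.2 also names the two arms, quinine in saline against saline.

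On analysis, section 6.5 says "Longitudinal linear mixed effects modeling will be used to examine the relationship between all outcome measures and treatment assignment", and sets the significance level with "For all analyses, alpha will be set to 0.05 (two-sided". The Study Summary is narrower: "Longitudinal linear mixed-effects models to evaluate pre- and post-treatment continuous outcome scores".

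Section 3.1 schedules two visits after baseline, at weeks 4 and 12. Neither is called primary.

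Section 6.4 sizes the trial on the width of a confidence interval for SNOT-22: "we estimate the required sample size to detect an effect with a precision of 10 (half the width of the desired 95% CI".

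**The concern.** A reader of the final report needs to know which comparison, at which visit, decides whether quinine worked. The documents name the arms but not the outcome, the visit or the model term (difference at week 4, difference at week 12, or an overall effect). They give no rule for how many primaries must succeed, no testing order and no adjustment.

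Without such a rule, the outcome and visit that carry the conclusion could be picked once the results are known. If one significant primary is then taken as success, the false-positive chance exceeds the 5% of a single test. Section 2 states an efficacy objective, and section 6.4 says the trial should guide later studies. A chance finding could therefore set the endpoint of the next trial.

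**Working it through.** **The plan's own figure.** Inputs from section 6.4: SD 20, target half-width 10, 95% interval. For a difference of two means, half-width = t(0.975, 2n−2) × 20 × √(2/n).

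- n = 31 per group: 2.000 × 5.080 = 10.16
- n = 32 per group: 1.999 × 5.000 = 9.995

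The stated 32 per group reproduces. SNOT-22 is the only outcome used for sizing.

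**How many primary tests.** If the Study Summary governs, only SNOT-22 and Lund-Kennedy among the primaries are continuous scores, which gives two tests. If section 6.5 governs, all four outcomes are modelled, which gives four. Subscales and a second visit would add more. Both counts are worked below, with one test per outcome.

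**Chance of at least one false result.** Assumptions: no true effect on any outcome, any one significant primary counts as success, and test statistics are normal with a common pairwise correlation r. The documents give no correlations, so 0, 0.7 and 0.9 are assumed. At r = 0 the formulas are 1 − 0.95^k in either direction and 1 − 0.975^k in quinine's favour. The other columns come from numerical integration.

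| Tests and direction | r = 0 | r = 0.7 | r = 0.9 | One test |
|---|---|---|---|---|
| 2, either direction | 1 − 0.95² = 9.8% | 8.4% | 7.0% | 5% |
| 2, favouring quinine | 1 − 0.975² = 4.9% | 4.2% | 3.5% | 2.5% |
| 4, either direction | 1 − 0.95⁴ = 18.5% | 13.0% | 9.4% | 5% |
| 4, favouring quinine | 1 − 0.975⁴ = 9.6% | 6.5% | 4.7% | 2.5% |

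If success required all the primaries to be significant, there would be no inflation.

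**Effect of the possible fixes on precision.** The ordinary 95% half-width for SNOT-22 is 10.0 at 32 per group. Section 4.3 assigns the first 10 patients to quinine without randomization. If they count within the 100, which is not stated, 90 are randomized, about 45 per arm, and the half-width is 1.987 × 4.216 = 8.4 before losses. Neither figure changes under a single primary on SNOT-22 or under Holm-adjusted tests. A 98.75% interval, which matches Holm's first step of 0.05/4 = 0.0125, would be 2.573 × 5.000 = 12.9 at 32 per group. Nothing in the documents asks for that interval.

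**The case against.** The strongest defence is that this is a phase II trial. Section 6.4 says there were no data for a power calculation, sizes on interval width, and presents the trial as a guide to later work. On that view, several outcomes reported as estimates need no strict error control, and the percentages above are illustrations rather than this trial's error rate. Much of this stands: the figures are conditional on a success rule the documents do not state. It does not dispose of the point, because section 2 sets an efficacy objective and section 6.5 attaches a significance level to every analysis.

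Four stronger readings are tempting, and the documents do not support them.

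- A reader might infer that four primary tests at 0.05 are settled, so that 18.5% is the error rate. The Study Summary supports only two modelled continuous primaries, and the two-test figures deserve at least equal weight.
- A reader might infer that the plan defers the choice until after unblinding. No section says so. Section 7.4 refers to an analysis plan, although the only one supplied, section 6.5, is silent here. The supportable statement is that nothing in the documents fixes the choice earlier.
- A reader might infer that rescue antibiotics will go untested, because section 6.5 says "Descriptive demographic data will be compiled including mean and median age, adjuvant therapy use, use of oral antibiotics, and microbiome profile". That sentence can be read simply as a description of the sample. The Study Summary wording is the better evidence that the number of tests is unclear.
- A reader might infer that keeping four primaries with Holm requires more patients. Holm adjusts the tests, whereas the target in section 6.4 is an ordinary 95% interval.

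**Conclusion.** The concern holds as an omission that should be corrected. The arms are named, but the lead outcome, primary visit, model term, success rule and multiplicity handling are not, and the number of primary tests is itself uncertain.

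Its size depends on two assumptions: that any one significant primary would be read as success, and that correlations lie between 0 and 0.9. On those terms the excess over a single test is modest with two tests and can be more than threefold with four independent tests (18.5% against 5%). These figures leave out the subscales and the second visit. The design's exploratory purpose makes this less serious than it would be in a confirmatory trial, but does not make it harmless.

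**What to change.** Before unblinding, amend sections 2.1, 3.2 and 6.5 to name one primary outcome, one visit and one treatment contrast, tested at two-sided 0.05. The SNOT-22 total score is a reasonable default because section 6.4 sizes on it. The choice belongs to the sponsor: the other outcomes also bear on the objective, and week 4 (end of irrigation) and week 12 (durability) answer different questions. Make the other outcomes, the SNOT-22 subscales and the other visit secondary, with estimates and 95% confidence intervals labelled supportive.

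This costs wording only: no new data and no new patients. If SNOT-22 is chosen, the 32 per group and the half-width of 10 stand. The real downside is that a nominal result on another outcome alone no longer counts as primary success.

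If all four stay primary, define one contrast for each and apply Holm to the four tests. This also needs no extra patients and leaves the ordinary 95% half-widths unchanged. Its cost is lower power per outcome, which cannot be computed because the documents give no effect size. The wider half-width of 12.9 arises only if 98.75% intervals are also wanted.
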